8.1. Overall Response Rate

ORR is defined as the proportion of patients whose best overall response is partial response or better based on each corresponding criterion. If data allow, ORR may be summarized with Clopper-Pearson 95% confidence intervals (CI). No confirmation is required for partial response or better.

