APPENDIX C: SUMMARY OF TUMOR ASSESSMENT CRITERIA

Table 1a: Comparison between RECIST 1.1 and irRC

Criteria	CR	PR	PD
RECIST 1.1	Disappearance of all target lesions. Any pathological lymph nodes (whether target or nontarget) must have reduction in short axis to <10 mm	At least a 30% decrease in the sum of diameters of target lesions, taking as reference the baseline sum diameters	At least a 20% increase in the sum of diameters of target lesions, taking as reference the smallest sum on study (this includes the baseline sum if that is the smallest on study). In addition to the relative increase of 20%, the sum must also demonstrate an absolute increase of at least 5 mm
			Note: the appearance of one or more new lesions is also considered progression.
irRC	Disappearance of all lesions in two consecutive observations not less than 4 weeks apart	≥50% decrease in tumor burden compared with baseline in 2 observations at least 4 weeks apart (as measured bi-dimensionally)	≥25% increase in tumor burden compared with nadir (at any single time point) in 2 consecutive observations at least 4 weeks apart, where Tumor Burden = SPD index lesions + SPD new, measurable lesions

Table 1b: Comparison between Cheson Criteria and LYRIC

Criteria	CR	PR	PD

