Cheson (Lugano)	PET-CT, score 1, 2, or 3* with or without a residual mass on 5PS† OR on CT, target nodes/nodal masses must regress to ≤ 1.5 cm in LDi	PET-CT score 4 or 5 with reduced uptake compared with baseline and residual mass(es) of any size. OR On CT $\geq 50\%$ decrease in SPD of up to 6 target measurable nodes and extranodal sites	
PET-CT score 4 or 5 with an increase in intensity of uptake from baseline and/or new FDG-avid foci consistent with lymphoma at interim or end-of-treatment assessment. OR On CT, an individual node/lesion must be abnormal with: LDi > 1.5 cm and increase by $\geq 50\%$ from PPD nadir and an increase in LDi or SDi from nadir 0.5 cm for lesions ≤ 2 cm 1.0 cm for lesions > 2 cm
 
In the setting of splenomegaly, the splenic length must increase by $> 50\%$ of the extent of its prior increase beyond baseline (eg, a 15-cm spleen must increase to > 16 cm). If no prior splenomegaly, must increase by ≥ 2 cm from baseline. New or recurrent splenomegaly
 
New or clear progression of preexisting nonmeasured lesions
 
Regrowth of previously resolved lesions
 
A new node > 1.5 cm in any axis or a new extranodal site > 1.0 cm in any axis; if < 1.0 cm in any axis, its presence must be unequivocal and must be attributable to lymphoma
 
Assessable disease of any size unequivocally attributable to lymphoma
 
AND/OR new or recurrent involvement of the bone marrow

LYRIC	Same as Cheson	Same as Cheson	
As with Lugano with the following exceptions:
 
IR
 
IR(1): $\geq 50\%$ increase in SPD in first 12 weeks
 
IR(2): $< 50\%$ increase in SPD with
 
a. New lesion(s), or
 
b. $\geq 50\%$ increase in PPD of a lesion or set of lesions at any time during treatment
 
IR(3): Increase in FDG uptake without a concomitant increase in lesion size meeting criteria for PD

Reference: Cheson BD, Ansell S, Schwartz L, et al. Refinement of the Lugano Classification lymphoma response criteria in the era of immunomodulatory therapy. *J Clin Oncol.* 2014; 32(27):3059-68

Table 2: Derivation of irRC overall responses

Measurable response	Nonmeasureable response		Overall response
Index and new, measureable lesions (tumor burden),^a %	Non-index lesions	New, nonmeasurable lesions	Using irRC
↓100	Absent	Absent	irCR ^b
↓100	Stable	Absent	irPR ^b
↓100	Unequivocal progression	Absent	irPR ^b
↓≥50	Absent/Stable	Absent	irPR ^b
↓≥50	Unequivocal progression	Absent	irPR ^b

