↓<50 to <25↑	Absent/Stable	Absent	irSD
↓<50 to <25↑	Unequivocal progression	Absent	irSD
≥25?	Any	Absent	irPD ^b

irCR=immune-related complete response; irPD=immune-related progressive disease; irRC=immune-related response criteria; irSD=immune-related stable disease

^a Decreases assessed relative to baseline, including measurable lesions only (>5 × 5 mm).

^b Assuming response (irCR) and progression (irPD) are confirmed by a second, consecutive assessment at least 4 weeks apart.

Reference:

Summary of Cheson Criteria

Revised Criteria for Response Assessment

Response and site	PET-CT-based response	CT-based response
Complete response	Complete metabolic response	Complete radiologic response (all of the following)
Lymph nodes and extralymphatic sites	Score 1, 2, or 3 with or without a residual mass on 5PS No extralymphatic sites of disease	Target nodes/nodal masses must regress to ≤ 1.5 cm in LD _i
Nonmeasured lesion	Not applicable	Absent
Organ enlargement	Not applicable	Regress to normal
New lesions	None	None
Bone marrow	No evidence of FDG-avid disease in marrow	Normal by morphology; if indeterminate, IHC negative
Partial response	Partial metabolic response	Partial remission (all of the following)
Lymph nodes and extralymphatic sites	Score 4 or 5 \dagger with reduced uptake compared with baseline and residual mass(es) of any size At interim, these findings suggest responding disease At end of treatment, these findings indicate residual disease	$\geq 50\%$ decrease in SPD of up to 6 target measurable nodes and extranodal sites When a lesion is too small to measure on CT, assign 5 mm x 5 mm as the default value When no longer visible, 0 x 0 mm For a node >5 mm x 5 mm, but smaller than normal, use actual measurement for calculation
Nonmeasured lesions	Not applicable	Absent/normal, regressed, but no increase
Organ enlargement	Not applicable	Spleen must have regressed by $>50\%$ in length beyond normal
New lesions	None	None

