In addition to the information presented in the statistical methods section of the protocol (Section 13) which provides the principal features of planned analyses for this study, this SAP provides appropriate statistical analysis methodologies in details. It also documents modifications or additions (if applicable) to the analysis plan that are not “principal” in nature and result from information that was not available at the time of protocol finalization.

PPD Biostatistics and Programming team, designee of Moderna Biostatistics and Programming department, will perform the statistical analysis of the efficacy, safety, pharmacokinetic, and pharmacodynamics; Statistical Analysis System (SAS) Version 9.4 or higher will be used to generate all statistical outputs (tables, figures, listings, and datasets). The SAP will be finalized and approved prior to the clinical database lock for primary analysis. If the methods in this SAP differ from the methods described in the protocol, the SAP will prevail.

2. Study Objectives

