7.3.4. Treatment Modifications

Number of patients with mRNA-2416 injection administered, number of patients without mRNA-2416 injection administered, reason for mRNA-2416 injection not administered, number of patients who had dose modified, categories of dose modification, reason for dose modified, number of lesion injected, and

lesion type will be summarized by scheduled visits, treatment arm and dose cohort for Phase I and Phase II, and total for each treatment arm combining Phase I and Phase II.

Number of patients with durvalumab administered, number of patients without durvalumab administered, action taken with durvalumab, and reason for action on durvalumab will be summarized by scheduled visits and dose cohort for Phase I and Phase II, and total for Arm B combining Phase I and Phase II.

8. Efficacy Analysis

All tables and figures for efficacy evaluations will be conducted using the activity evaluable set by treatment arm and dose cohort (as specified in Section 3.3) for Phase I and Phase II, and total for each treatment arm combining Phase I and Phase II. Listings will be based on the safety set.

Solid tumor response will be assessed by investigators based on RECIST 1.1 (complete response [CR], partial response [PR], stable disease [SD], progressive disease [PD], or not evaluable [NE]), and based on irRC (immune-related complete response [irCR], immune-related partial response [irPR], immune-related stable disease [irSD], immune-related progressive disease [irPD], or not evaluable [NE]). Lymphoma response will also be assessed by investigators based on Cheson 2014 criteria (positron emission tomography [PET]-CT-based complete metabolic response, partial metabolic response, no metabolic response, or progressive metabolic response; CT-based complete radiologic response, partial radiologic response, SD, or PD), and based on LYRIC (PET-CT-based complete metabolic response, partial metabolic response, no metabolic response, progressive metabolic response, or indeterminate response; CT-based complete radiologic response, partial radiologic response, SD, PD, or indeterminate response). Best overall response is determined from time-point overall response. When SD for RECIST 1.1 or irSD for irRC is believed to be the best overall response, it must meet the minimum time (at least 55 days between the first dose date and the last SD assessment date, and no PD between). Death may be considered in determination of best overall response.

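### SAP 8.1 waives response confirmation for every criterion, so the exploratory irRC response rate may count single-scan responses that fall short of the protocol's irRC definition

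*SAP*

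**What the plan says.** SAP 8.1 gives one definition of ORR for all response criteria: "ORR is defined as the proportion of patients whose best overall response is partial response or better based on each corresponding criterion". The same paragraph ends: "No confirmation is required for partial response or better". SAP 8 lists ORR per irRC/LYRIC among the efficacy endpoints, next to ORR per RECIST 1.1/Cheson 2014, and says: "Best overall response is determined from time-point overall response". It sets a minimum time for SD and irSD but no two-observation rule for irCR or irPR.

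Protocol Appendix C Table 1a defines irRC complete response as "Disappearance of all lesions in two consecutive observations not less than 4 weeks apart". It defines irRC partial response as a 50% or greater "decrease in tumor burden compared with baseline in 2 observations at least 4 weeks apart". Table 2 of the same appendix derives the overall irRC response and attaches footnote b to the irCR, irPR and irPD rows. The footnote reads: "Assuming response (irCR) and progression (irPD) are confirmed by a second, consecutive assessment at least 4 weeks apart".

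SAP 1 settles precedence: "If the methods in this SAP differ from the methods described in the protocol, the SAP will prevail". SAP 13 lists one change to the planned analysis, the dropping of an exploratory correlation endpoint.

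**The concern.** The irRC response categories in the protocol are not single-scan categories: the repeat observation is part of what irCR and irPR mean. A waiver covering every criterion removes that part for irRC while the output keeps the irRC label. A reader of the study report would take the rate to be irRC response as the protocol defines it.

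The stake is limited. The irRC ORR is exploratory (protocol 7.6, SAP 3.2.3). What is at risk is the interpretability of that one rate, and its reproducibility: two programmers working from the same text, one applying Appendix C and one applying SAP 8.1 literally, could report different numbers.

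**Working it through.** The plan gives no figure on this point to reproduce, so the check is mainly a comparison of texts.

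**1. Does the waiver reach irRC?** SAP 8.1 defines ORR for each criterion in use, SAP 8 lists irRC as one of them, and the waiver names no exception. So it does.

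**2. Which criteria does it conflict with?**

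| Criterion | Confirmation in the protocol's definition of CR/PR | Conflict with SAP 8.1 |
|---|---|---|
| RECIST 1.1 (Appendices C and D) | None stated | No |
| Cheson 2014 (Appendix C) | None stated | No |
| LYRIC (Appendix C Table 1b) | "Same as Cheson" | No |
| irRC, CR (Table 1a) | Two consecutive observations, 4 weeks or more apart | Yes |
| irRC, PR (Table 1a) | Two observations, 4 weeks or more apart | Yes |

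The conflict is confined to irRC. Appendix C also has a loose end of its own. Footnote b of Table 2 asks for a consecutive second assessment and is marked on the irPR rows, although its words name only irCR and irPD. Table 1a asks for consecutive observations for irCR but not for irPR.

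**3. Which text governs?** Under SAP 1 the SAP does. With best overall response taken from time-point responses and no confirmation step, one time-point irPR is enough to make a responder.

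**4. Direction and size.** Every response that meets Table 1a also counts under SAP 8.1, but not the reverse. The SAP rate can therefore only equal or exceed the protocol-defined rate. Each unconfirmed responder adds 1/n. At the planned evaluable numbers in SAP 4.1:

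- Arm A, both stages: 1/27 = 3.7 points
- Arm B, both stages: 1/41 = 2.4 points
- Arm A, stage 1 only: 1/13 = 7.7 points
- Arm B, stage 1 only: 1/15 = 6.7 points

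SAP 8 also reports efficacy by dose cohort and by arm across phases, so the actual step depends on each table's denominator.

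The total effect cannot be computed, because neither document gives a confirmation rate. As an assumption only, let 90% to 50% of single-scan irRC responses be confirmed later. A single-scan rate of 0.20 would then become 0.20 × 0.9 = 0.18 down to 0.20 × 0.5 = 0.10, and a rate of 0.25 would become 0.225 down to 0.125. If all are confirmed, the effect is zero.

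**5. Can the protocol definition be applied with the planned scans?** Protocol 10.10 schedules assessments every 56 days, plus or minus 7. The first two windows are days 49 to 63 and 105 to 119. The gap is between 105 − 63 = 42 and 119 − 49 = 70 days, always more than 28. The next scheduled scan meets the four-week condition.

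**6. Are the Phase II designs touched?** The exact probability of success is the sum, over first-stage counts x that allow continuation, of P(X1 = x) × P(X2 ≥ r − x), where r is the number of responses needed in total.

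- Arm A (13 then 14 patients; at least 1, then at least 4 responses): 0.0416 at a true rate of 0.05 and 0.801 at 0.20.
- Arm B (15 then 26 patients; at least 2, then at least 8 responses): 0.0430 at 0.10 and 0.803 at 0.25.

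Both agree with the stated 0.05 and 0.80. The Phase II primary endpoint is RECIST 1.1 response, so the irRC rule does not enter these figures.

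**The case against.** The best defence is that confirmation may already be in the data. SAP 8 has investigators assess response by irRC category, and protocol 10.10 uses the local investigator's assessment for the irRC analysis. If investigators follow Appendix C and record irCR or irPR only once both observations are in, SAP 8.1 merely says that the programmer adds no further step. The reference to each corresponding criterion fits that reading. This lowers certainty but does not remove the conflict: neither document states that recording rule, and SAP 8 builds best response from time-point responses. If the phrase did import the irRC definition, the waiver in the same paragraph would contradict it.

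The absence of this change from SAP 13 is weak evidence on its own, because SAP 1 says that the SAP as a whole documents modifications. That is fair, and the point does not depend on SAP 13.

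It is also fair that the endpoint is exploratory and that 1/n is a step per patient, not an estimate of bias. Both hold, and they make this a minor point.

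**Conclusion.** The conflict is real and narrow. As written, SAP 8.1 allows the exploratory irRC ORR to include single-scan responses that do not meet the protocol's definition of irCR or irPR. Any bias is upward, 1/n per unconfirmed responder (3.7 points at n=27, 2.4 at n=41), and it is zero if no such responder occurs. This assumes that time-point irRC responses are recorded without waiting for the second observation, which the documents leave open.

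Two stronger readings do not follow:

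- A reader might infer that the primary ORR, and with it the error rates of the Simon designs, is inflated. The protocol's RECIST 1.1 summaries state no confirmation condition, so the waiver contradicts nothing in the documents there.
- A reader might infer that one unconfirmed irPR could open stage 2, because protocol 8.2.5 and 8.2.6 count responses by RECIST v1.1 or iRECIST. That requires iRECIST to mean irRC. Neither document defines iRECIST, both use irRC by name elsewhere, and SAP 8.1 defines a reported rate, not an enrolment rule.

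**What to change.** In SAP 8.1, limit the no-confirmation sentence to RECIST 1.1, Cheson 2014 and LYRIC. Count irCR and irPR as Appendix C Table 1a defines them: consecutive observations for irCR, and two observations four or more weeks apart for irPR. First reconcile Table 1a with footnote b of Table 2, so that it is clear whether the irPR observations must also be consecutive. Show unconfirmed irRC responses in a separate row.

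If an unconfirmed irRC rate is what the sponsor intends, label it as unconfirmed in the outputs and list it in SAP 13.

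The cost is one clause, one reconciliation and one table row, with no added visits. The downside is that the irRC ORR may be lower than under the current text, and a response first seen at a patient's last scan cannot be confirmed. The separate row keeps such responses visible.

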8.2. Duration of Response

DOOR is defined as the time from first response (partial response or better) to first occurrence of a disease progression.

For patients who do not experience any of these events by the last date of study participation, death date, or the time of data cutoff, whichever is the earliest, the following censoring rule will be used for DOR:

- Patients who do not experience disease progression and have an adequate post-baseline tumor assessment will be censored at the date of the last adequate tumor assessment that is SD or better.
- Patients who do not experience disease progression and do not have any adequate post-baseline tumor assessment that is SD or better will be censored at Day 1.

Patients who never achieve a response will be excluded from this analysis.

DOR (days) = date of event/censoring - date of first response + 1.

If data allow, swimmer plots of tumor assessment over time such as time to response and DOR (per RECIST 1.1 and irRC, respectively) may be provided for each patient by treatment arm.

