13.4.3 EFFICACY ANALYSES

The Activity Evaluable Population will be used for the analyses of efficacy data based on the dose of mRNA-2416 received.

Best response will be determined for each patient in accordance with RECIST 1.1, and Cheson guidelines and the objective response rate presented for each dose cohort. The overall objective response rate based on irRC or LYRIC will also be determined. The disease control rate based on RECIST 1.1 will also be

determined for Phase II patients. Progression-free survival and durability of response will be determined using Kaplan-Meier methodology. Please refer to [Appendix C and D](#) for a description of “Immune-related Response Criteria,” and RECIST 1.1 criteria.

The details of Simon’s two-stage study design and analysis used for Arm A and Arm B Phase II will be included in the Statistical Analysis Plan (SAP).

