Listings will be provided for tumor assessment of target lesions, non-target lesions, new lesions, and overall response evaluation. Waterfall plots of best percent change from baseline in sum of diameters of target lesions based on investigator assessments (per RECIST 1.1 and irRC, respectively) will be provided by treatment arm, and by treatment arm and injection status, respectively.

The following efficacy endpoints will be analyzed:

- ORR based on RECIST 1.1/Cheson 2014 criteria
- ORR based on irRC/LYRIC
- DOR based on RECIST 1.1/Cheson 2014 criteria
- PFS based on RECIST 1.1/Cheson 2014 criteria
- PFS based on irRC/LYRIC
- DCR based on RECIST 1.1

All derived efficacy parameters will be displayed in a data listing.

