8.3. Progression-free Survival

PFS is defined as the time from first dose to first occurrence of a disease progression or death, whichever comes first.

For patients who do not experience one of these events by the last date of study participation or the time of data cutoff, the following censoring rule will be used for PFS:

- Patients who do not experience disease progression or death and have an adequate post-baseline tumor assessment will be censored at the date of the last adequate tumor assessment that is SD or better.
- Patients who do not experience disease progression or death and do not have any adequate post-baseline tumor assessment that is SD or better will be censored at Day 1.

PFS (days) = date of event/censoring - date of first dose + 1.

PFS will be summarized by descriptive statistics (mean, standard deviation, minimum and maximum). The Kaplan-Meier method will be used to estimate the distribution functions of PFS per RECIST 1.1 and irRC, respectively. The quartiles, median along with 95% CI of PFS, and probability of being event free at selected time points will be provided. Kaplan-Meier plot of PFS (per RECIST 1.1 and irRC, respectively) will be provided for Arm A regardless of mRNA 2416 dose level in each study phase.

Kaplan-Meier plot of PFS (per RECIST 1.1 and irRC, separately) will be provided for Arm B regardless of mRNA 2416 dose level in each study phase.

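### SAP 8.2 censors deaths in duration of response, SAP 8.3 leaves treated patients who die unscanned out of PFS, and a raw mean of censored PFS times is reported

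*SAP*

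**What the plan says.** **DOR.** SAP 8.2: "DOOR is defined as the time from first response (partial response or better) to first occurrence of a disease progression". Its censoring rules cover patients without an event "by the last date of study participation, death date, or the time of data cutoff, whichever is the earliest". Those with an adequate post-baseline assessment are censored at the last one showing SD or better. A second rule, for "Patients who do not experience disease progression and do not have any adequate post-baseline tumor assessment that is SD or better", censors at Day 1. SAP Section 8 lists "DOR based on RECIST 1.1/Cheson 2014 criteria" among the endpoints to be analyzed, but the only DOR display that 8.2 names is optional: "swimmer plots of tumor assessment over time such as time to response and DOR". Protocol 13.4.3 states: "Progression-free survival and durability of response will be determined using Kaplan-Meier methodology".

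**PFS.** SAP 8.3: "PFS is defined as the time from first dose to first occurrence of a disease progression or death, whichever comes first". SAP Section 8 runs all efficacy tables and figures on the activity evaluable set, which SAP 4.3.3 limits to dosed patients with at least one tumor response evaluation. The set comes from protocol 13.4.1 and 13.4.3. SAP 8.3 adds "PFS will be summarized by descriptive statistics (mean, standard deviation, minimum and maximum"), followed by Kaplan-Meier quartiles, median with CI and event-free probabilities.

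**Related text.** SAP 8.1 defines response under each criterion and waives confirmation for all of them. Protocol Appendix C defines irCR and irPR by two observations at least 4 weeks apart. SAP Sections 8 and 8.4 require at least 55 days from first dose for SD to count. DOR, PFS and disease control rate (DCR) are secondary endpoints in Phase II, and the irRC response rate is exploratory.

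**The concern.** Death in a responder ends the response; it is not ignorable loss to follow-up. Censoring it makes DOR estimate time to progression as if nobody died first, and the Kaplan-Meier curve assumes that the dead had the same outlook as those still followed. The next section of the same SAP treats death as a failure, so the two secondary endpoints disagree on what a death means.

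For PFS, time starts at first dose and death is an event, yet entry to the analysis depends on a later scan. The patients removed are those who fail earliest. Both features push the same way: DOR and PFS look longer whenever deaths occur without a scan.

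The raw PFS mean fails differently. It counts each censoring time as if it were a progression or death, so it falls as censoring rises and says little about PFS itself.

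**Working it through.** **Plan's own figures.** The only powered figures are the Simon designs in protocol 13.2. With P(active) = sum over stage-1 counts x1 that pass of Bin(x1; n1, p) × P(stage-2 responses ≥ threshold − x1):

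| Arm | Rule | Exact alpha | Exact power |
|---|---|---|---|
| A | ≥1 of 13, then ≥4 of 27; 0.05 vs 0.20 | 0.0416 | 0.8011 |
| B | ≥2 of 15, then ≥8 of 41; 0.10 vs 0.25 | 0.0430 | 0.8029 |

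Both reproduce. They are stated for evaluable patients, so nothing below changes them.

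**1. DOR.** Assumptions: 400,000 simulated responders; exponential times, median 168 days; scans every 56 days with uniform jitter of ±7 days (the window in protocol 10.10); progression dated at the next scan. Deaths without progression are either censored at the last scan (SAP 8.2) or counted. Kaplan-Meier at day 175 (25 weeks):

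| Share of terminal events that are deaths without PD | SAP rule | Death as event | Difference |
|---|---|---|---|
| 10% | 0.528 | 0.498 | 0.030 |
| 20% | 0.561 | 0.498 | 0.063 |
| 30% | 0.595 | 0.494 | 0.101 |

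Expected responders at the design alternatives: 27 × 0.20 = 5.4 and 41 × 0.25 = 10.25. Deaths censored at shares of 10 to 30%: 0.5 to 1.6 and 1.0 to 3.1. Binomial standard errors near 50%: sqrt(0.25/5.4) = 0.215 and sqrt(0.25/10.25) = 0.156.

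The Day 1 rule in 8.2 is inert. Only responders are analyzed, and the response scan is itself SD or better.

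**2. PFS set.** If a share u of treated patients die unscanned before time t, S_evaluable(t) = S_treated(t)/(1 − u). For a true 40%:

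| u (assumed) | 1/(1 − u) | PFS reads |
|---|---|---|
| 3% | 1.03 | 0.412 |
| 5% | 1.05 | 0.421 |
| 10% | 1.11 | 0.444 |

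The ORR denominator behaves the same way. At the Arm A threshold, 4/27 = 14.8%; one treated, unscanned death gives 4/28 = 14.3% on all treated patients, and three give 4/30 = 13.3%.

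**3. Raw PFS mean.** With exponential event times and independent censoring, mean observed time ÷ true mean = share of patients with an event. At 20% censored the mean is about 20% low, and at 40% about 40% low (simulated ratios 0.80 and 0.60).

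**Lesser points.** SD minimum: protocol 10.10 permits scans at 56 ± 7 days, that is 49 to 63. Days 49 to 54 miss the minimum, 6 of 15 permitted days. Under the 2-day visit window in the Schedule of Events (54 to 58), only day 54 misses, 1 of 5. These count days, not patients, and matter only when that scan is the patient's last SD. The SAP gives no category for an SD that misses the minimum.

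**The case against.** **Size.** The death shares are not in the documents, and the DOR shift is below one standard error. The plan also limits unscanned deaths: a 12-week life expectancy criterion, a tumor assessment at End of Treatment, scans at 90 and 180 days, and imaging whenever progression is suspected. All of this stands, and it argues for a small effect. It does not remove a bias that runs in one direction and costs little to avoid.

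**Is 10% a ceiling for u?** A reader might take Arm A's allowance (30 enrolled for 27 evaluable) as an upper bound. It is not. It is a planning figure, actual losses can exceed it, and it runs from enrolled to evaluable patients, so it can include some who were never treated.

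**Is the primary analysis untouched, or invalid?** A reader might infer either, and neither is supported. The Simon design is written for evaluable patients, so its error rates and thresholds stand. The reported ORR nevertheless uses the same set and omits the same patients.

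**Has Kaplan-Meier been dropped for DOR?** A reader might infer so from the silence of SAP 8.2. The SAP introduction says the SAP adds to protocol Section 13 and prevails where methods differ. Silence is not a difference, so the protocol method stands.

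**Is the irRC response rate ambiguous?** Appendix C and the waiver in SAP 8.1 disagree, but the precedence clause makes the waiver govern. What remains is a departure that SAP Section 13 does not declare.

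**Does the Day 1 rule in 8.3 imply a wider PFS set?** No. A patient inside the set whose only scans are not evaluable can meet it.

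**Conclusion.** Three defects hold on the text. DOR censors deaths that PFS counts. PFS excludes treated patients who die before any tumor evaluation. The PFS mean and SD treat censored times as events. The first two lengthen the reported secondary endpoints.

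The size is unknown. Under the assumed 10 to 30% death shares, exponential times and a 168-day median, 25-week DOR reads about 3 to 10 points high, against standard errors of about 22 points (Arm A) and 16 points (Arm B). PFS is overstated by 1/(1 − u), with u assumed. The raw mean is a presentation fault, because valid Kaplan-Meier summaries are planned beside it. The undeclared irRC waiver, the inert Day 1 rule and the 55-day SD minimum are lesser points.

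**What to change.** **SAP 8.2:** define DOR as time from first response to first progression or death from any cause. Remove the death date from the censoring lead-in, delete the Day 1 rule, and restate the Kaplan-Meier method already in protocol 13.4.3.

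**SAP 8.3:** run PFS on all treated patients and record the change of analysis set in SAP Section 13. Reconcile the cohort grouping at the same time: SAP 4.3.3 groups by enrolled cohort, whereas protocol 13.4.3 analyzes efficacy by dose received. Delete the PFS mean and SD and keep the planned Kaplan-Meier summaries.

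**Lesser items:** for irRC, either apply the Appendix C confirmation or declare the unconfirmed rate in SAP Section 13. Reconcile the 55-day SD minimum with the scan windows in protocol 10.10 and the Schedule of Events, and state the category for an SD that misses it.

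**Cost:** a SAP amendment before database lock, with no new scans or patients. DOR and PFS will read somewhat shorter. Treated patients who are alive but never scanned enter PFS censored at Day 1 and add no information. If irRC confirmation is applied, a first response at the last scan cannot be confirmed and that rate may fall.
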